2.3 Secondary Outcomes

Due to the secondary nature of the analyses, there will be no adjustment for type I error. However, it is important to note that all these comparisons are pre-specified and results of all the performed comparisons will be reported.

2.3.1 ICD acceptance at 7 days in the racially concordant vs. discordant video.

Pearson chi-square test will be used to test whether there is a difference in the proportion of patients accepting ICD implantation (yes vs. no/unsure) between concordant video group and discordant video group. The Fisher Exact Test will be used if necessary. In addition to a p-value, we will provide the estimate of difference in proportions and 95% confidence interval (CI).

2.3.2 Changes in knowledge score.

Outcome definition: To test the hypothesis that a patient centered educational video can improve patients' knowledge of SCD and ICDs, a 13-item questionnaire is developed to assess knowledge of SCA and ICD therapy. This short questionnaire comprises true/false statements designed to measure participants' comprehension of SCD, associated risk factors, and treatment options including ICD therapy. Possible scores vary from 0 to 13, with a higher score indicating better knowledge. To assess the change in knowledge, the same questionnaire will be administered immediately before (pre) and after (post) the exposure to the video or UC. Additionally, participants will be contacted at 7 days post enrollment, and the same questionnaire will be administered to assess retention of information.

Analysis method: To determine the effect of the video on knowledge of SCD and ICDs, two-tailed t-test (or Wilcoxon rank sum test if substantial departure from normality is noted) will be used to test whether there is a difference in the mean changes in knowledge score pre- and post-exposure between combined video group and usual care group. In addition to p-value we will provide the estimate and 95% confidence intervals of the difference in the changes in knowledge score (after minus before exposure) between combined video group and usual care group. We will also compare within groups the pre- and post-values, as well as 7-day values.

2.3.3 Changes in decisional conflict scale (DCS).

Outcome definition: We will use the DCS to measure decisional conflict. The scale measures a person's perception of the difficulty in making a decision, the extent to which they feel uncertain about treatment options, are knowledgeable about the risks and benefits of options, clear about personal values, and supported in decision making. Higher scores indicate greater decisional conflict and patients experiencing decisional conflict are more likely to change their minds, delay decisions, express regret, and fail knowledge tests. Patients will be administered the DCS **pre**-intervention at the baseline enrollment visit and **post** intervention at 7 days post enrollment. Respondents will be asked to reflect on their decision and respond to the DCS questions using a 5-point Likert scale. Responses to each statement are scored 0 (strongly agree) to 4 (strongly disagree). Total scores range from 0 to 100, with higher scores indicating greater decisional conflict.

Analysis method: **We will compare change in DCS from baseline to 7-days (post minus pre)** between the video intervention and usual care groups using independent samples t -test or Wilcoxon rank sum test if substantial departure from normality is noted. In addition to p-values, we will provide the estimate and 95% confidence intervals of the difference in DCS pre- and post-exposure for the both groups. We will also compare across treatment groups the pre- and post-exposure DCS values. The DCS change will also be compared between the racially concordant and discordant video groups.

2.3.4 Comparison of ICD implantation status at 90 days from study enrollment.

To determine the differences in implantation rates in the video intervention versus UC arms, the difference in the proportion of patients with an ICD implanted within 90 days of study enrollment between combined video intervention arm and UC arm will be compared using the Pearson chi-square test. If necessary, the Fisher Exact Test will be used. In addition to a p-value, we will provide the estimate of difference in proportions and the 95% confidence interval (CI). We will also compare ICD acceptance at 7 days and implantation status at 90 days, overall and within randomized groups. We will use the McNemar test due to correlation of the ICD acceptance and implantation status within a patient. The above analyses will be repeated for comparison of the racially concordant and discordant video groups as well.

2.3.6 Patient-Provider time comparison.

Patient-Provider time (in minutes) will be compared between the video intervention and usual care groups, as well as between concordant and discordant video groups. We will use independent samples t -test or Wilcoxon rank sum test if substantial departure from normality is noted. In addition to p-values, we will provide the estimate and 95% confidence intervals of the patient-provider time in the groups.

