Sample size and power estimation: Sample size and power estimates are based on the findings from the pilot study results for black participants. In the pilot study, among black patients, there was an improvement in the number of correct responses on the knowledge

questionnaire from baseline to post intervention in both the video and the UC arms, mean standard deviation (SD) 8.4 ± 2.7 to 10.8 ± 2.1 (video group), 7.4 ± 3.9 to 9.7 ± 2.9 usual care (p-value comparing video and UC NS). Based on these data and considering two-tailed equal variances t-test and 0.05 type I error, a sample size of 480 patients will have 99% power or higher to detect a mean test score difference between arms of 1.5 with SD equal to 2.5, 3.0, or 3.5. For a mean difference between video and usual care arms equal to 1.0, power remains at 99%, 93%, and 84%, respectively across SD of 2.5, 3.0 or 3.5.

DECISIONAL CONFLICT SCALE

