We will use the DCS to measure decisional conflict. The scale measures a person's perception of the difficulty in making a decision, the extent to which they feel uncertain about treatment options, are knowledgeable about the risks and benefits of options, clear about personal values, and supported in decision making; the scale has demonstrated good reliability (Cronbach's alpha coefficients > 0.78) and predictive validity. Higher scores indicate greater decisional conflict and patients experiencing decisional conflict are more likely to change their minds, delay decisions, express regret, and fail knowledge tests. Patients will be administered the DCS *pre* intervention at the baseline enrollment visit, and post intervention, 1-week post enrollment. Respondents will be asked to reflect on their decision and respond to the DCS questions using a 5-point Likert scale. Responses to each statement are scored 0 (strongly agree) to 4 (strongly disagree). Total scores range from 0 to 100, with higher scores indicating greater decisional conflict. **Analysis Plan:** To determine differences in decisional conflict, each group's scores will be compared using independent samples t-test at two time points or Wilcoxon rank sum test if substantial departure from normality is noted. The first comparison will be within group (pre and post intervention) followed by 2) between group differences in the change scores using analysis of covariance (ANCOVA) that adjust for baseline scores. All quantitative tests will be two-sided and conducted at the 5% level of significance. Due to the secondary nature of these comparisons, there will be no adjustment for type I error. However, it is important to note that all these group comparisons are pre-specified and results of all attempted comparisons will be reported.

Sample size estimates:

In the pilot study, among black patients, the mean and standard deviation DCS scores for UC and video groups were 36.0 ± 3.2 and 33.7 ± 4.3 respectively. Based on these data and considering two-tailed equal variances t-test and 0.05 type I error, a sample size of 480 patients will have 99% power or higher for a mean DCS difference between arms of 3.0 across standard deviations of 2.5-5.0. For a mean difference between video and usual care arms equal to 1.0, SD 2.5, power remains at >99%.

ICD IMPLANTATION RATES

Compare the proportion of patients with an ICD implanted within 90 days of study enrollment in UC vs. combined video group.

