1.5 Sample Size Justification

Note: The primary outcome sample size computations were originally based on two co-primary comparisons (video vs. usual care and concordant vs. discordant video) with the Bonferroni adjustment for type I error by specifying two-tailed 0.025 type I error ($0.025=0.05/2$) for each of the two above comparisons. Due to challenges with enrollment, prior to data lock and unbinding, a single primary comparison of video vs. usual care was chosen and type I error of 0.05 will be used.

The primary outcome is proportions of patients accepting ICD implantation in video vs. usual care (UC) groups at 1 week after baseline visit. The sample size has been determined to provide a reasonable level of confidence for detecting clinically important differences in decision of ICD implantation between groups if such differences indeed exist. *In the pilot study 60% of black patients in the video group indicated yes for ICD placement compared with 43% in the UC arm.* We estimated a 15-20% increase in the proportion of patients indicating yes for ICD implantation in the video group could change practice patterns. Considering the above UC proportion of 43%, with total of 309 analyzable subjects with equal spread into the UC, concordant video, and discordant video groups (i.e. 103 patients in each of the three randomized groups) there is 91% power to detect 20% absolute increase in the combined video group, and 80% power to detect 17% absolute increase.

2. Statistical Analysis

All analyses will be conducted using SAS version 9.4 or higher software (SAS Institute Inc., Cary, NC) and R version 3.5.3 (R Foundation for Statistical Computing, Vienna, Austria). A p-value <0.05 will be considered as statistically significant.

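### The continuous secondary outcomes switch between an unspecified t-test and a Wilcoxon test with no stated criterion, and the plan omits a between-group interval for provider time

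*SAP*

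**What the plan says.** SAP 2.3.2 (knowledge change, combined video versus usual care) specifies a "two-tailed t-test (or Wilcoxon rank sum test if substantial departure from normality is noted) will be used to test" a difference in mean change, and promises a 95% CI for that between-group difference. SAP 2.3.3 (DCS change) and 2.3.6 (patient-provider time) use "independent samples t -test or Wilcoxon rank sum test if substantial departure from normality is noted". None of the three sections defines a substantial departure, and none says whether the t-test pools the variances.

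A variance assumption appears only in the protocol's power paragraphs for knowledge and DCS, each "considering two-tailed equal variances t-test and 0.05 type I error". The protocol's pilot knowledge scores are "8.4 ± 2.7 to 10.8 ± 2.1 (video group), 7.4 ± 3.9 to 9.7 ± 2.9 usual care". Its pilot DCS SDs are 3.2 (usual care) and 4.3 (video).

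For the between-group DCS comparison the protocol specifies "between group differences in the change scores using analysis of covariance (ANCOVA) that adjust for baseline scores", which the SAP does not carry over. The interval in SAP 2.3.3 is worded as a pre/post difference for each of the two groups. For provider time, SAP 2.3.6 states that "we will provide the estimate and 95% confidence intervals of the patient-provider time in the groups".

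SAP section 2 sets the threshold: "A p-value <0.05 will be considered as statistically significant". SAP 2.3 adds: "Due to the secondary nature of the analyses, there will be no adjustment for type I error".

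**The concern.** Three things are left open.

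- **The test is settled after the data are seen.** SAP 2.3 supports the lack of multiplicity adjustment by noting that the comparisons are pre-specified, yet which test produces each p-value is not. The switch is foreseeable for knowledge: the score is capped at 13 and the pilot post-video mean was 10.8 with SD 2.1, so the ceiling lies (13 − 10.8)/2.1 = 1.05 SD above the mean. If the switch happens, the p-value comes from a test that does not address a difference in means, while the reported interval does. The two could disagree.
- **The t-test variant matters at 2:1.** A pooled t-test is too liberal when the smaller group has the larger SD, and too conservative when the larger group does. The pilot shows the first pattern for knowledge and the second for DCS.
- **Two intervals do not match their objectives.** SAP 1.2 asks whether minutes with the clinician differ between arms, but 2.3.6 plans intervals only within arms. SAP 2.3.3 compares change between arms, but its interval is worded as change within each arm.

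**Working it through.** **Inputs.** Group sizes 206:103 (SAP 1.5: 309 analyzable patients, 103 per arm, two video arms combined); the protocol's planned sizes are 320:160. Two-sided level 0.05. Pilot score SDs, video / usual care: knowledge before 2.7 / 3.9, knowledge after 2.1 / 2.9, DCS 4.3 / 3.2. The documents give no SD of change, no pre-post correlation, no pilot sample size and no SD for provider time.

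**1. The plan's own figure.** Protocol power for a knowledge difference of 1.0 at 320:160 is 99%, 93% and 84% for SD 2.5, 3.0 and 3.5. With SE = SD × √(1/320 + 1/160) and power = Φ(1/SE − 1.96):

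- SD 2.5: SE 0.2421, power 98.5%
- SD 3.0: SE 0.2905, power 93.1%
- SD 3.5: SE 0.3389, power 83.9%

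The stated figures are reproduced, under equal SDs.

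**2. Pooled t-test with unequal SDs.** The pooled variance is s² = [205·SD_V² + 102·SD_U²]/307. The SE the test assumes is √[s²(1/206 + 1/103)]. The true SE is √[SD_V²/206 + SD_U²/103]. Type I error = 2·[1 − Φ(1.96 × assumed/true)].

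| SDs, video / usual care | Assumed SE | True SE | Assumed/true | Type I error |
|---|---|---|---|---|
| Knowledge before, 2.7 / 3.9 | 0.3801 | 0.4279 | 0.888 | 8.2% |
| Knowledge after, 2.1 / 2.9 | 0.2891 | 0.3210 | 0.901 | 7.8% |
| DCS, 4.3 / 3.2 | 0.4789 | 0.4349 | 1.101 | 3.1% |

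At 320:160 the results agree to within rounding.

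**3. Simulation.** Normal data, equal means, 206:103, 40,000 replicates. The two-stage rule takes Wilcoxon if an omnibus normality test has p < 0.05 and the pooled t-test otherwise; that rule is an assumption, since the SAP names none.

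| SDs | Pooled t | Welch | Wilcoxon | Two-stage |
|---|---|---|---|---|
| Knowledge before | 8.2% | 4.9% | 6.7% | 8.1% |
| Knowledge after | 7.7% | 4.9% | 6.5% | 7.7% |
| DCS | 3.1% | 4.9% | 3.9% | 3.3% |
| Equal SDs (3 / 3) | 5.1% | 5.0% | 5.0% | 5.1% |

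With equal groups of 103:103 and SDs 2.1 / 2.9, all four lie between 4.9% and 5.2%. With an assumed gamma-type skew, unequal SDs and equal means, Wilcoxon rejects in 20% (knowledge-after SDs) and 14% (DCS SDs) of samples, while Welch rejects in 5.2% and 4.7%.

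**4. From score SDs to change SDs.** The test is on change, so the relevant quantity is SD(change) = √(SD_pre² + SD_post² − 2r·SD_pre·SD_post). The correlation r is not given. For knowledge, under assumed values:

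| r video / r usual care | SD change, video / usual care | Ratio, usual care to video | Pooled-t type I error |
|---|---|---|---|
| 0.5 / 0.5 | 2.46 / 3.51 | 1.43 | 8.1% |
| 0.5 / 0.75 | 2.46 / 2.58 | 1.05 | 5.4% |
| 0.3 / 0.7 | 2.88 / 2.79 | 0.97 | 4.8% |
| 0.7 / 0.5 | 1.94 / 3.51 | 1.81 | about 10% |

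The range for knowledge is therefore about 5% to 10%. The DCS has only one pilot SD per arm, so the same step cannot be done there.

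**5. Provider time.** No SD is available, so no error rate can be computed. The point rests on the text: ICD acceptance (SAP 2.2, 2.3.1), knowledge change (2.3.2) and 90-day implantation (2.3.4) each have a between-group difference with a 95% CI, and 2.3.6 does not.

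**The case against.** A reader might infer that whichever test is used, the error rate will be wrong. The documents do not support that.

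- The SAP says only t-test. Welch fits that wording and holds about 5%. Equal variances is a power-calculation assumption in the protocol, not an analysis instruction.
- The pilot SDs are for scores, not changes. The knowledge SDs already differed before the intervention, so that gap is not a video effect, and the post-intervention SDs come from the same arms and are not independent support. Some correlations remove the problem altogether.
- Wilcoxon holds 5% when the two distributions are identical. The 6% to 7% and 4% figures are against a null of equal means with unequal spread.
- Choosing the test from the data did no harm in itself in the simulation with equal SDs; with unequal SDs and normal data it tracked the pooled t-test.
- If the per-group estimates for provider time are means, the difference and its standard error can be worked out from the two intervals, so it would be too strong to say that no estimate of the difference is recoverable.
- These are secondary outcomes with no adjustment claimed.

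All of this stands, and it makes the error-rate point conditional. It leaves three gaps: the variant and the trigger are unspecified, the fallback does not match the reported interval, and 2.3.6 does not plan the estimate that its objective calls for.

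**Conclusion.** The concern holds as a gap in specification. That the test is chosen without a criterion, that the t-test variant is unstated, and that 2.3.3 and 2.3.6 have mismatched intervals all follow from the text alone.

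The size of any error-rate distortion rests on two assumptions: a pooled t-test, and change-score SDs that differ between arms as the pilot score SDs do. Under both, type I error is about 8% for knowledge (about 5% to 10% over the correlations tried) and about 3% for DCS, against about 5% for Welch. Wilcoxon would give about 6% to 7% and 4% against equal means. The distortions run in opposite directions, so they cannot be waved off as conservative.

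The primary chi-square test is untouched. So is the planned 1:1 concordant versus discordant comparison as regards error rate. This is a free or cheap improvement, not a threat to the trial's main conclusion.

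**What to change.** - **SAP 2.3.2, 2.3.3 and 2.3.6:** name the Welch t-test, with its 95% CI for the between-group mean difference, as the single pre-specified analysis. Keep Wilcoxon as a sensitivity analysis, reported whatever the distribution looks like.
- **SAP 2.3.3:** reconcile with the protocol's baseline-adjusted ANCOVA and state which analysis is definitive. If ANCOVA is kept, use robust standard errors. Reword the interval as the between-group difference in change.
- **SAP 2.3.6:** add the between-group difference in mean minutes with its 95% CI.

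The cost is a few lines of SAP text, and the results are standard software output. The downside is a negligible loss of efficiency if variances are equal, and possibly lower power than Wilcoxon if the data are heavily skewed.

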As a secondary outcome, we will compare the proportions of individuals saying yes to ICD implant in the racially concordant video (A) and the racially discordant video (B). The two proportions will be compared with the Pearson chi-square test. We do not expect small counts in light of the pilot study results but, if necessary, the Fisher Exact Test will be used. In addition to p-value we will provide estimates of proportions with their confidence intervals (exact confidence intervals will be used if needed). At an interim analysis based on the rate of patient accrual and projected sample size, the effect of racial concordance on the decision for ICD implantation was changed from a co-primary outcome to a secondary outcome.

KNOWLEDGE QUESTIONNAIRE

To test the hypothesis that a patient centered educational video can improve patients' knowledge of SCD and ICDs we developed a questionnaire to assess knowledge of SCA and ICD therapy. This short (13-item) questionnaire comprises true/false statements designed to measure participants' comprehension of SCD, associated risk factors, and treatment options including ICD therapy. Possible scores vary from 0 to 13, with a higher score indicating better knowledge. Potential answers for each question are (true, false or don't know); “don't know” answers will receive a score of 0 while correct true and false responses will receive a score of 1. In the pilot study the test had excellent reliability with a correlation coefficient of 0.9. To assess the change in knowledge, the same questionnaire will be administered immediately before and after the exposure to the video or UC. Additionally, participants will be contacted at 1-week post enrollment, and the same questionnaire will be administered to assess retention of information.

Analysis plan: To determine the effect of the video on knowledge of SCD and ICDs: The pre/post intervention *mean* change in correct responses will be compared between combined video groups (N=320) and usual care group (N=160). Comparisons of these continuous measures will be performed with a two-tailed t-test (or Wilcoxon rank sum test if substantial departure from normality is noted).

Outcomes: Mean and standard deviation of correct answers on the knowledge questionnaire pre and post intervention in the combined video group with UC.

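### The knowledge outcome is tested on raw post-minus-pre change without baseline adjustment, which is valid but on the pilot SDs gives about 1.8 to 2.2 times the variance of ANCOVA

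*SAP*

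**What the plan says.** SAP 2.3.2 (Changes in knowledge score) specifies a two-tailed t-test, or a Wilcoxon rank sum test if normality clearly fails, which "will be used to test whether there is a difference in the mean changes in knowledge score pre- and post-exposure between combined video group" versus the usual care (UC) group. The protocol's analysis plan under Knowledge Questionnaire agrees: the mean pre/post "change in correct responses will be compared between combined video groups (N=320) and usual care group (N=160"), again by t-test or Wilcoxon. Neither document gives a baseline-adjusted model for this outcome.

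The protocol does plan an analysis of covariance adjusting for baseline under Decisional Conflict Scale. SAP 2.3.3 names only a t-test or Wilcoxon test on change for that scale.

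The protocol gives the pilot knowledge scores (mean ± SD, range 0 to 13) as "8.4 ± 2.7 to 10.8 ± 2.1 (video group), 7.4 ± 3.9 to 9.7 ± 2.9 usual care". Its power statement says that "a sample size of 480 patients will have 99% power or higher to detect a mean test score difference between arms of 1.5" at SDs of 2.5, 3.0 or 3.5, and continues: "For a mean difference between video and usual care arms equal to 1.0, power remains at 99%, 93%, and 84"%. Those three figures belong to the same three SDs in turn. The statement covers 480 patients only. SAP 1.5 now plans on 309 analyzable patients for the primary outcome and does not restate power for knowledge.

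**The concern.** A change score subtracts the whole baseline value, so it fixes the slope of post on pre at 1. That is efficient only if the true slope is close to 1. Here the score is capped at 13 and the pilot SD falls after exposure in both arms (2.7 to 2.1 and 3.9 to 2.9). Patients who start high have little room to gain, and the slope must be well below 1. The change score therefore over-corrects for baseline and carries baseline noise into the treatment comparison.

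What is at stake is precision on whether the video teaches better than counselling, and sensitivity of the estimate to chance baseline imbalance. The loss matters more if fewer than 480 patients are analysed.

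**Working it through.** **1. The plan's own figures.** Inputs, from the protocol's knowledge power paragraph and analysis plan: "considering two-tailed equal variances t-test and 0.05 type I error", 320 video and 160 UC patients. Power = Φ(δ / (SD × √(1/320 + 1/160)) − 1.96), with √(1/320 + 1/160) = 0.0968.

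- δ = 1.0: 98.5%, 93.1% and 83.9% at SD 2.5, 3.0 and 3.5 (stated 99, 93, 84).
- δ = 1.5: above 99.9%, 99.9% and 99.3% (stated 99 or higher).

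The stated powers reproduce.

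**2. Inputs for the comparison.** Pilot SDs: video 2.7 pre, 2.1 post; UC 3.9 pre, 2.9 post. The pre-post correlation r is not reported, nor is the SD of change. The coefficient of 0.9 in the protocol is a reliability figure, not the correlation across an intervention. I take r as an assumption, equal in both arms, and show 0.3 to 0.9.

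**3. Formulas.** Per arm:

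- Var(change) = SDpre² + SDpost² − 2r·SDpre·SDpost
- Var(ANCOVA) = SDpost² + b²·SDpre² − 2b·r·SDpre·SDpost

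The pooled slope at 2:1 allocation is b = r × (2×2.7×2.1 + 3.9×2.9) / (2×2.7² + 3.9²) = r × 22.65/29.79 = 0.76r. It is below 1 at every possible r. SE² of the effect is the video variance over its n plus the UC variance over its n.

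**4. Worked case, r = 0.5, 206/103.**

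- Change: video 7.29 + 4.41 − 5.67 = 6.03; UC 15.21 + 8.41 − 11.31 = 12.31. SE² = 6.03/206 + 12.31/103 = 0.149, so SE = 0.386.
- ANCOVA (b = 0.38): video 3.31; UC 6.31. SE² = 3.31/206 + 6.31/103 = 0.077, so SE = 0.278.
- Variance ratio = 1.93. The difference detectable with 80% power is 1.08 points on change and 0.78 with ANCOVA.

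**5. Across r.** Power for a 1.0-point difference, change vs ANCOVA:

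| r | Variance ratio | 320/160 | 206/103 |
|---|---|---|---|
| 0.3 | 2.17 | 79% vs 98% | 60% vs 90% |
| 0.5 | 1.93 | 90% vs 99% | 74% vs 95% |
| 0.7 | 1.79 | 98% vs >99% | 90% vs 99% |
| 0.9 | 1.98 | both >99% | both >99% |

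A simulation of 4,000 trials at 206/103 gave ratios of 1.92 (r = 0.5) and 1.81 (r = 0.7).

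**6. Floor.** With k = SDpre/SDpost, the within-arm ratio is 1 + (k − r)²/(1 − r²), whose minimum over r is k². That is (2.7/2.1)² = 1.65 for video and (3.9/2.9)² = 1.81 for UC. For the combined effect with a common r, the minimum is 1.78, at r = 0.75.

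**7. Chance imbalance.** At 206/103 the SE of the baseline difference is √(2.7²/206 + 3.9²/103) = 0.43 points. The change-score estimate differs from the ANCOVA estimate by (1 − b) times the baseline difference. For b from 0.68 (r = 0.9) down to 0.23 (r = 0.3), a one-SE imbalance moves it by 0.14 to 0.33 points.

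**The case against.** The strongest reply is that nothing here is an error. Under randomisation the change-score test is unbiased and holds its type I error. It is pre-specified alike in both documents, it answers the SAP's objective as worded (a larger pre-to-post improvement), and it concerns a secondary outcome. All of that stands. It does not restore the lost precision, and adjustment does not alter the question: regressing change, or the post score, on arm and baseline gives the same arm coefficient.

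The power loss is also conditional. At 320/160 and r = 0.5 the planned test still has 90%, and near r = 0.9 the choice makes no practical difference to power. The 309 is the planned number for the 7-day decision. The post-exposure knowledge score is taken before the baseline visit ends, so more patients may have it. The 206/103 column is therefore an assumption; the variance ratio does not depend on the total number.

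Two stronger readings are tempting. A reader might infer that the protocol's knowledge power is wrong; it reproduces. A reader might also infer that raw change hid a real video effect in the pilot. The changes were 2.4 and 2.3, a difference of 0.1, while the post-exposure difference was 10.8 − 9.7 = 1.1 and the baseline difference 8.4 − 7.4 = 1.0. An adjusted difference of 1.1 − b × 1.0 would be about 0.4 to 0.9. That range rests on an assumed r and on a pilot whose size is not given in the text reviewed and whose comparison was reported as not significant. It illustrates how imbalance acts and is not evidence of an effect.

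**Conclusion.** The point holds as a loss of efficiency, not of validity. On the pilot SDs, the planned knowledge analysis has about 1.8 to 2.2 times the variance of a baseline-adjusted analysis for r between 0.3 and 0.9, and about 1.8 times or more at any correlation common to both arms. The power cost for a 1.0-point difference is material at low to moderate r, particularly if the analysed number is nearer 309 than 480, and negligible near r = 0.9.

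This rests on the pilot SDs taken at face value, one correlation and one slope for both arms, and normal-approximation power. The exact factor cannot be read from the documents, because it needs the pre-post correlation. The change is recommended, but the planned test would not invalidate a conclusion.

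**What to change.** In SAP 2.3.2, and in the matching analysis plan under Knowledge Questionnaire in the protocol so that the two stay aligned, make the main knowledge analysis a linear model of post-exposure score on arm (combined video vs UC) with the pre-exposure score as covariate and robust standard errors. Report the adjusted mean difference with its 95% CI. Keep the change-score comparison, with its t-test or Wilcoxon choice, as a sensitivity analysis. Specify this before unblinding.

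The cost is a short edit in each document and a few lines of code. Both scores are already collected at the same visit, so no new data are needed.
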